CLINICAL INVESTGATIONAL PLAN (CIP)

Clinical Investigation Title:	Zip Arthroplasty Patient Satisfaction Evaluation
Clinical Investigation Acronym:	ZAPS
Clinical Investigation Number:	011
	ZipLine Medical, Inc.
	[name]
Study Sponsor	[name]
	[contact]
	[contact]
Principal Investigator:	[name]
	Montgomery Orthopaedic Assocs
Study Conton(s)	[name]
Study Center(s):	[name]
	[name], Clinical Research Consultant
Medical Monitor:	for ZipLine Medical, Inc.
	[contact] / [contact]

Revision History

Date	Author	Changes
2-Oct-2017	[name]	Initial Release

1 Protocol Synopsis

Study Purpose:	To evaluate patient satisfaction of closure method used after joint knee arthroplasty		
Study Design:	Prospective, randomized, single center study to evaluate Zip Closure Device in subjects undergoing knee arthroplasty.		
Study Endpoints	Primary: Patient and Observer Scar Assessment Scale (POSAS) at 6 weeks post procedure.		
	Secondary: Subject Experience and Satisfaction results at 6 weeks post procedure.		
Subject Population:	Patients identified as candidates for knee arthroplasty and meet the study selection criteria		
Number of Subjects	40		
Number of Sites	Single Center		
Study Procedure:	Closure Method used immediately after Arthroplasty		
Device Name:	Zip Surgical Closure Device		
Duration of Study	Anticipated enrollment duration to meet sample size: Total Duration of Study:		
5 II . II 6 I . I I	,		
Follow-Up Schedule	3 weeks and 6 weeks post arthroplasty surgery		
Inclusion Criteria	Patients undergoing primary elective knee arthroplasty.		
	2. Willing and able to provide informed consent and/or obtain legal guardian authorization		
	3. Willing and able to comply with the subject-specific requirements outlined in the study protocol		
Exclusion Criteria	Patients that do not meet the conditions listed in the wound closure device warnings, precautions, and contraindications (Appendix A)		
	2. Patients with comorbidities or conditions that the investigator deems to be ineligible for the study		
	3. Patients without the capacity to give informed consent (e.g., dementia)		
	ineligible for the study		

Table of Contents

1	P	rot	tocol	Synopsis	. 2
2	I	ntr	oduc	tion	. 5
	2.1		Back	ground	. 5
	2.2		Purp	ose of the study	. 5
3		Dev	ice D	escription	. 6
	3.1		Dev	ce Overview	. 6
4	F	≀eg	ulato	pry Status	. 7
	4.1		The	Zip Surgical Skin Closure is a FDA Class I, 510(k) Exempt Device	. 7

2.1 Background

Sutures and metal staples are considered standard of care methods for surgical skin closure. The Zip® Surgical Skin Closure device from ZipLine Medical, Inc. (Campbell, CA USA) is a more recent method of skin closure that utilizes skin adhesive and adjustable ratcheting straps to achieve and maintain tension necessary for wound closure and healing. The Zip device was designated Class I, 510(k) Exempt by the US FDA in 2010, and the CE Mark was affixed in 2014. Clinical studies comparing the Zip device to staples and sutures have demonstrated several benefits, including:

- Fewer wound-related readmissions compared to staples on TKA patients¹
- Can eliminate a home health nurse visit compared to staples on TKA patients²
- 3x faster wound closure compared to subcuticular sutures on pacemaker patients³
- Superior cosmetic scar quality compared to subcuticular suture for pediatric cardiac sternotomy patients⁴
- Less patient pain during removal compared to subcuticular suture (Prolene®) for pediatric cardiac sternotomy patients⁵
- Superior protection of wound from extrinsic distraction forces compared to sutures⁶

Limited patient-reported satisfaction data exists for the Zip device as compared to staples and sutures, so this study will attempt to address this need.

2.2 Purpose of the study

To evaluate patient satisfaction of closure method used after knee joint arthroplasty. Metal staples and the Zip® Surgical Skin Closure device are approved methods in regular use. Selection of method is generally based on physician preference. This study is to determine what, if any, differences exist in patient satisfaction amongst the two methods.

¹ [name]., [name]., Alejandro Gonzalez [name]., [name]. Hospital for Special Surgery - New York City, USA. Novel Non-Invasive Secure Skin Closure Following Total Knee Arthroplasty Leads to Fewer Wound Complications and No Patient Home Care Visits Compared to Surgical Staples. Presented at 2015 ISTA Conference, Vienna, Austria October 1, 2015
² ibid.

³ LALANI, G. G., SCHRICKER, A. A., SALCEDO, J., HEBSUR, S., HSU, J., FELD, G. and BIRGERSDOTTER-GREEN, U. (2016), Cardiac Device Implant Skin Closure with a Novel Adjustable, Coaptive Tape-Based Device. Pacing and Clinical Electrophysiology. Accepted Author Manuscript.

⁴ Tanaka Y1, Miyamoto T2, Naito Y2, Yoshitake S2, Sasahara A2, Miyaji K3. Randomized Study of a New Noninvasive Skin Closure Device for Use After Congenital Heart Operations. Ann Thorac Surg. 2016 May 31. pii: S0003-4975(16)30204-1. doi: 10.1016/j.athoracsur.2016.03.072. [Epub ahead of print]

⁵ ibid.

⁶ Levi K, Ichiryu K, Kefel P, et al. (October 12, 2016) Mechanics of Wound Closure: Emerging Tape-Based Wound Closure Technology vs. Traditional Methods. Cureus 8(10): e827. DOI 10.7759/cureus.827

3 Device Description

3.1 Device Overview

ZipLine Medical, Inc. has developed a novel, non-invasive skin closure device called "Zip Surgical Skin Closure" to replace sutures, staples and glue for closure of the skin layer for surgical incisions or laceration repair. The device is designed to provide closure speed superior to sutures, while resulting in a suture-like cosmetic outcome. Both pre-clinical feasibility study data and feedback from over 2000 human cases during the device's commercial use in the USA suggest that these design intentions are correct. This study will test these assertions in a controlled clinical setting, with the goal of providing results with statistical significance.

The Zip device is a single use, sterile medical device.

Figure 1. Zip Surgical Skin Closure Device

The Zip Surgical Skin Closure Device is applied to clean, dry skin after deeper tension-relieving (i.e., dermal or subcutaneous) sutures have been applied.

The device adheres to the skin adjacent to an incision by use of pressure-sensitive skin adhesives. A combination of acrylic and hydrocolloid adhesives are used to provide a skin-friendly environment while providing the necessary tack to maintain skin adhesion during the recommended wear time of the device. The Zip device will be placed on the incision as the surgeon approximates the incision edges and tensions the wound by adjusting the ratcheting straps located along the device. Once the desired tension is achieved, the excess strap ends are trimmed with scissors, and a conventional absorptive dressing may be applied. The Zip will remain on the skin for 3 weeks, at which point it will be removed.

[figure not shown]

Figure 2. Adjusting Incision Closure Tension

After application, patients may shower (but not soak in a tub or pool) with the device on. The device is removed by lifting the edge of the device and gently peeling along the incision, taking care not to apply stress to the incision. If there is a risk of skin stripping, an adhesive removal agent may be used during removal.

[figure not shown]

Figure 3. Key Components of the Zip Surgical Skin Closure Device

In addition to the pressure-sensitive adhesives, the device's closure and force distribution components are made up of polyurethane monofilm, polyethylene tape, polyester and nylon.

4 Regulatory Status

4.1 The Zip Surgical Skin Closure is a FDA Class I, 510(k) Exempt Device.

In 2010, ZipLine Medical, Inc. submitted a "513(g)" request for product classification to the U.S. Food and Drug Administration (FDA). In July 2010, ZipLine Medical received a letter from the FDA indicating that FDA reviewers "believe the ZipLine 1 System falls within Title 21 of the Code of Federal Regulations (CFR) 880.5240, Medical adhesive tape and adhesive bandage (Product Code- KGX). A Medical adhesive tape and adhesive bandage is a Class I type device, exempt from the premarket notification [510(k)] requirements of the Act, subject to the limitations of the exemption found in 21 CRF 880.9."

4.2 Quality System Regulations

The Zip Surgical Skin Closure Devices have been developed and are manufactured in full compliance with FDA Title 21 CFR Part 820 Quality System Regulations, including design controls, document controls, purchasing controls, identification and traceability, production and process controls, acceptance activities,

nonconforming product, corrective and preventive action, labeling and package control, handling, storage, distribution and installation, record keeping, servicing, and statistical techniques.

Origin of Manufacture: The Zip® brand Surgical Skin Closure Devices are manufactured in the USA.

Company Registration: ZipLine Medical, Inc. is registered with the FDA in compliance with Title 21 Code of Federal Regulations (CFR) Part 807, Subparts A-D.

4.3 Indication For Use

The Zip Surgical Skin Closure Device is indicated for use during and after skin incision procedures to approximate skin and hold together the skin edges until healing can take place

5 Study Design

Prospective, randomized, single center, study to evaluate Zip Closure Device in subjects undergoing knee arthroplasty.

5.1 Study Population

Patients identified as candidates for knee arthroplasty and meet the study selection criteria.

5.2 Sample Size

Knee Arthroplasty of 40 subjects will be enrolled. 20 subjects will receive ZipLine and 20 subjects will receive Staples.

5.3 Statistical Analysis Plan

General Summary

All variables of interest including subject demographics, baseline characteristics, POSAS scores and patient satisfaction of closure method used will be summarized descriptively by assigned closure groups. Mean, standard deviation, range, and Coefficient of Variation (CV) will be reported across the POSAS Scale attributes, plus comparative "t" test applied between the treatment groups across POSAS attributes. Results will include significance testing (t test) for Knee Arthroplasty study.

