6.6 Study Evaluations and Assessments

The following assessments will be made during each study visit:

Subject Satisfaction Questionnaire – to evaluate subject experience and outcome of incision closure

POSAS (Patient and Observer Scar Assessment Scale) – the subject and investigator will rate commonly described scar characteristics from a patient and observers perspective.

Table 1: Schedule of Assessments

Assessments	Screening / Baseline	Study Procedure	3-Week Follow-Up (+/- 3 days)	6-Week Follow-Up (+/- 7 days)
Screen and Informed Consent Process	Х			
Medical Hx, Demographics, Eligibility	Х			
Randomization Assignment	Х			
Study Procedure and Closure Method		Х		
Subject Satisfaction Questionnaire			Х	Х
POSAS: Subject and Impartial rater Assessment			х	х
Photo of closure of incision		Х	Х	Х
Adverse Event review			Х	Х
Study Exit				Х

7 Subject Compensation

Participating study subjects will not incur any costs as a result of participating in the study and will not receive reimbursement or payments for participation.

8 Study Withdrawal

Subjects may be terminated or withdrawn from the study for the following reasons:

- Voluntary withdrawal meaning that the subject voluntarily chooses not to further participate in the study
- Lost to follow-up meaning that the subject is more than one month late (beyond the late visit window) to a study visit and 3 documented attempts to contact the subject are unsuccessful. A subject who misses a study visit but attends a subsequent visit will no longer be considered lost to follow-up.
- In the physician's opinion, it is not in the best interest of the subject to continue study participation.
- Subject death.

Any study subject who does not attend a scheduled follow-up visit should be contacted by site personnel to determine the reason for the missed appointment(s). The reason for the missed visit should be determined and documented in the subject's study records. All subjects enrolled (including those withdrawn or lost to follow-up) shall be accounted for with appropriate documentation.

9 Adverse Events

Adverse events (AEs) may occur during the procedure phase or the follow-up phase of the study. Adverse events occurring after the baseline assessment but before the arthroplasty procedure will be documented in the subject's medical record but will not count as related to the closure device.

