Each adverse event will be recorded in the corresponding subject's CRF. Each adverse event will be judged by the Investigator as to its relationship and level of relatedness to the closure device. In addition, the Investigator will identify the date of onset, severity and duration of the AE. All adverse events will be monitored until they are adequately resolved or explained. If a subject reaches the final follow-up visit and is experiencing a new or ongoing adverse event, the study sponsor should be contacted to discuss the need and/or methods for continued surveillance of the event.

The Investigator must submit to the Sponsor a report of any Serious Adverse Event (SAE), Serious Adverse Device Effect (SADE) or Unanticipated Adverse Device Effect (UADE) within 24 hours of knowledge of the event.

Sponsor Contact: [name]
[contact]
[contact]

Email: [contact]

In addition, the Investigator will report adverse events to the reviewing IRB / EC (as applicable) according to the local reporting requirements.

10 Study Size Determination

Knee Arthroplasty: 2 groups: Zipline to Staples (2 groups, paired data) with POSAS Scale data est. delta \sim 1.5, and Est. SD \sim 1.41

Alpha error = .05

Power = 0.9, sample n = 19 pairs, or 38 total subjects with estimated 5% subject study loss, n = 40 total subjects, or 20 per group.

11 Methods and Procedures

- 1. Study investigator and designated staff shall be trained on study procedures by the sponsor or sponsor delegate.
- 2. Patients shall be screened prior to surgery for study eligibility by the investigator or staff member designated by the investigator.
- 3. Eligible patients shall be presented with the study opportunity during a pre-operative consultation visit to the study site, and will be given the opportunity to read the informed consent form and receive answers to any questions about the study. If the patient is able and willing to participate, they will sign the consent form and become an enrolled subject.
- 4. Randomization will be assigned in permuted block so that even numbers of each closure method is assigned
- 5. Immediately after the arthroplasty procedure the assigned closure method will be applied and documented on the procedure data form

- 6. During the subject's scheduled (i.e., standard of care) 3-week post-operative clinic visit and immediately AFTER the wound closure device is removed (e.g., Zip or staples), clinic staff will:

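### No single 6-week POSAS score is named as primary, and the attribute-wise t tests carry no multiplicity rule, so the 5% level is not protected

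*Combined protocol and SAP*

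**What the plan says.** - **Endpoint.** The synopsis (Section 1, Study Endpoints) reads "Primary: Patient and Observer Scar Assessment Scale (POSAS) at 6 weeks post procedure". It fixes the instrument and the visit, but not the score.
- **Components.** Section 6.6 says that "the subject and investigator will rate commonly described scar characteristics from a patient and observers perspective". There are therefore at least two rater perspectives, each covering several characteristics. Table 1 and Section 11 (steps 6b and 7b) describe the observer as an impartial rater rather than the investigator.
- **Analysis.** Section 5.3 says that descriptive statistics "will be reported across the POSAS Scale attributes" and, in the same sentence, plans a t "test applied between the treatment groups across POSAS attributes". It names no primary score, rater, summary measure, visit or testing order.
- **Sample size.** Section 10 describes the comparison as "2 groups, paired data) with POSAS Scale data est. delta" of about 1.5 with an SD of about 1.41, and sets "Alpha error = .05" and power 0.9. This gives 19 pairs, 38 subjects, and 40 after 5% loss. It does not say which POSAS score the delta and SD describe.
- **Multiplicity.** No section contains an adjustment, a hierarchy or a success criterion.

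**The concern.** A primary endpoint has to reduce to one variable and one test, or to several tests with a rule that combines them. Here the visit is fixed and the variable is not. The descriptive statistics in the same Section 5.3 sentence are given per attribute, so the natural reading of the test is also one per attribute. A single test on a combined score is not excluded, but it is not specified either.

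Two consequences follow. Each t test keeps its own 5% level, so the chance that at least one is falsely significant is above 5%, and nothing in the plan prevents that one from being presented as the primary result. And if attributes or raters disagree, for instance if the subject's rating favours one closure and the observer's does not, there is no pre-specified reading. A score chosen after the data are seen cannot repair either problem.

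**Working it through.** **1. Reproduce the sample size.** Inputs from Section 10: delta 1.5, SD 1.41, alpha 0.05, power 0.90. Sidedness is not stated.

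Two independent groups, two-sided, normal approximation:

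n per group = 2 × (1.960 + 1.282)² × (1.41/1.5)² = 18.57, so 19.

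Then 2 × 19 = 38, and 38/0.95 = 40. This matches the plan. A one-sided test gives 16 per group. A paired calculation taking 1.41 as the SD of differences gives 10 pairs (normal) or 12 pairs (t). The stated 19 is thus the size for **one** two-sided, unpaired test at 0.05, with 1.41 as the per-group SD.

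**2. Chance of at least one false positive.** Neither the number of tests k nor their correlation is in the documents; both are assumed. For independent tests the formula is 1 − 0.95^k:

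- k = 2: 1 − 0.9025 = 0.098
- k = 6: 1 − 0.7351 = 0.265
- k = 12: 1 − 0.5404 = 0.460

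For correlated attributes, 100,000 null trials were simulated with 19 per group, equicorrelated normal attributes and two-sided t tests at 0.05:

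| Correlation | k = 2 | k = 6 | k = 12 |
|---|---|---|---|
| 0.9 | 7.1% | 11.1% | 13.8% |
| 0.7 | 8.4% | 16.7% | 23.8% |
| 0.5 | 9.2% | 21.0% | 32.4% |
| 0 (formula) | 9.8% | 26.5% | 46.0% |

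Every cell exceeds 5%, including two scores correlated at 0.9. These rates apply if any significant test may count as the primary result.

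**3. Power once one score is named.** Noncentral t, 19 per group, delta 1.5:

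| SD | Alpha | Power |
|---|---|---|
| 1.41 (Section 10) | 0.05 | 89.1% |
| 1.8 (assumed) | 0.05 | 70.5% |
| 2.0 (assumed) | 0.05 | 61.4% |
| 1.41 (Section 10) | 0.025 | 82.2% |

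The last row is the first Holm step if both rater scales are primary. The middle rows only illustrate sensitivity: moving from an attribute to a total would normally change delta as well as SD.

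**The case against.** **The inflation depends on a rule the plan does not state.** No section says that any significant attribute counts as success. Section 10 has one alpha, one delta and one SD, and 19 reproduces as a single test, which suggests that one comparison was in mind. On that reading the error rate is 5%, provided the score is fixed before analysis. This stands as a limit on the figures, which are conditional. It does not close the gap, because the score is still not fixed anywhere.

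**The study is small and low-stakes.** It has 40 subjects at one center and a Class I device. Section 2.2 asks what differences in satisfaction exist, and Section 12 calls the study a survey rather than an experiment. Section 3.1 does state a "with the goal of providing results with statistical significance", but the claims it refers to are closure speed against sutures and a suture-like cosmetic result; the comparator here is staples and closure speed is not an endpoint. That sentence is weak support and the point does not need it. Section 5.3 itself calls for significance testing, the synopsis labels POSAS as primary, and Section 10 powers it at 90%.

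**The power figures assume that 1.41 is a per-group SD.** Section 10 speaks of paired data. If 1.41 were an SD of differences, the per-group SD would be 1.41/√2 ≈ 1.00 at within-pair correlation 0, or 1.41/√0.6 ≈ 1.82 at 0.7 (both correlations assumed), with power of about 99% or 70%. The per-group reading is the better one, since it alone reproduces 19, but it remains an assumption.

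**Conclusion.** The concern holds. The primary hypothesis is not reduced to a single variable, the only comparative rule on its natural reading runs several unadjusted 5% tests, and the stated power cannot be tied to any one of them. The omission is certain from the text. The size of the inflation is conditional: about 7% to 46% across 2 to 12 tests and correlations from 0.9 to 0, if any significant test may be taken as the primary result. The number of tests and the correlations are assumptions. This should be settled before any analysis, because afterwards the choice of score can no longer be made credibly.

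**What to change.** **Section 5.3 and the synopsis.** Before analysis, name one 6-week POSAS score as primary, stating the rater scale and one scoring rule; the choice is the sponsor's (for example, the subject-scale total). Test it once with a two-sided independent-samples t test at 0.05 and report the mean difference with its 95% CI. Label the individual attributes, the other rater's scale and the 3-week scores as supportive, reported as estimates with CIs. If both rater scales must be primary, use Holm.

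**Section 10.** State which score delta 1.5 and SD 1.41 describe, and check that they apply to the named primary score. If they do not, restate delta, SD and the power for 19 evaluable subjects per group. Correct the paired wording to two independent groups.

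**Section 6.6.** If the observer scale is chosen, reconcile the investigator in the text with the impartial rater in Table 1 and Section 11.

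**Cost.** Wording, plus a check of the sample-size inputs. An isolated significant attribute can no longer be claimed as a primary result. Enrollment stays at 40 if the Section 10 inputs apply, with 89% power by the exact t test. With two primary scales under Holm, power at the first step is 82% per score, again if those inputs apply to both.

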5.4 Study Criteria

There will be no gender-based enrollment restrictions. It is expected that the proportion of male to female subjects will be similar to the normal proportion related to the procedure type.

No vulnerable subjects shall be considered for enrollment. This includes children, pregnant women, nursing home residents or other institutionalized persons, students, employees, fetuses, prisoners, and persons with decisional incapacity.

There will be no restrictions on subject age.

There will be no restrictions or selection criteria based on subject racial and ethnic distribution.

5.4.1 Inclusion Criteria

Candidates for the study must meet all the following criteria:

- 1. Patients undergoing primary elective knee arthroplasty.
- 2. Willing and able to provide informed consent and/or obtain legal guardian authorization

3. Willing and able to comply with the subject-specific requirements outlined in the study protocol

5.4.2 Exclusion Criteria

Candidates for the study must not meet any of the following criteria. If any one of the following is met, the patient is not eligible to participate in the study.

- 1. Patients that do not meet the conditions listed in the wound closure device warnings, precautions, and contraindications (Appendix A)
- 2. Patients with comorbidities or conditions that the investigator deems to be ineligible for the study
- 3. Patients without the capacity to give informed consent (e.g., dementia)

6 Study Phases

The study will be conducted in phases as subjects are consented, determined eligible by meeting the study selection criteria, receive treatment and followed as standard after the arthroplasty procedure and exited from the study

